#### **5.4.2.8. Overall survival rate (OS%)**

See Section 4.1.2.8 for the definition of 6/9/12/15/18-month survival rates.

The 6/9/12/15/18-month survival rates are analyzed by Kaplan-Meier method, and the corresponding 95% CIs are calculated using the log-log transformation according to normal distribution approximation with back transformation to CIs on the untransformed scale.

#### **5.4.2.9. Time to treatment failure (TTF)**

See Section 4.1.2.9 for the definition of time to treatment failure (TTF).

Secondary endpoint TTF is calculated in months by using the following formula:  $(\text{TTF event date/censoring date} - \text{date of first administration} + 1) / 30.4375$ .

Kaplan-Meier method is used to analyze TTF, and the median TTF (month) is calculated. Brookmeyer-Crowley method is used to estimate the two-sided 95% CI of median time, and the survival curve is drawn.

At the same time, the number and percentage of TTF events as well as the censoring number and percentage are calculated.

### **5.4.3. Exploratory analyses**

See Section 5.4.5.

### **5.4.4. Subgroup analysis**

In order to evaluate whether the efficacy of this study is consistent among various subgroups, ORR, PFS (evaluated by IRC based on RECIST v1.1), and OS in the following subgroups are analyzed based on FAS. ORR, PFS, OS and 95% CI of each subgroup are estimated, and forest plot of ORR is drawn. The analysis method is the same as those in Sections 5.4.1 and 5.4.2:

- Age (< 65 years, ≥ 65 years)
- Gender (male, female)
- Baseline ECOG PS (0 points, 1 point)
- Extrahepatic metastasis (yes, no)
- Vascular invasion (yes, no)
- Child-Pugh score (5 points, 6 points)
- BCLC stage (stage B, stage C)
- Weight (< 60 kg, ≥ 60 kg)
- HBV infection (yes, no)
- Baseline alpha fetoprotein level (< 400 ng/mL, ≥ 400 ng/mL)
- Baseline alpha fetoprotein level (< 200 ng/mL, ≥ 200 ng/mL)

### **5.4.5. Other analyses**

Based on FAS, the best post-baseline changes in the sum of target lesion diameter values from baseline over time is plotted (i.e. waterfall plot, which is grouped by the best overall response).

Based on FAS, the swimmer plots of objective response and disease control are drawn. A swimmer plot of treatment and survival status of subjects who continue treatment after PD is drawn.

Based on FAS, the consistency of imaging PD events in each group is analyzed according to the consistency analysis of IRC and investigator assessment (LE) among different populations. Similar analyses are carried out for CR/PR consistency and BOR consistency of imaging assessment in each group.

Based on FAS, the change of target lesions of subjects with best overall response of CR/PR/SD (assessed by IRC based on RECIST v1.1) from baseline over time is plotted (i.e., spider plot).

Based on FAS, the change of target lesions of subjects who continue study drug therapy after PD (assessed by investigators based on RECIST v1.1) from baseline against time is plotted (i.e., spider plot).

Based on FAS, HBsAg loss is defined as the number and percentage of subjects who have positive baseline value and any negative post-baseline test values.

Based on FAS, the overall survival curve is plotted according to different populations and grouped by CR + PR, SD, and PD according to best overall response (best overall response is assessed by IRC based on RECIST v1.1, excluding subjects with the best overall response of NE).

The information of subsequent post-withdrawal anti-cancer therapy (including chemotherapy, radiotherapy, target therapy, surgery, interventional procedure, traditional Chinese medicine, and other categories) used after treatment discontinuation is summarized to analyze whether the anti-cancer therapy used after treatment discontinuation in each population is balanced, and listed. In addition, the duration (month) of a particular category of subsequent post-withdrawal anti-cancer therapy (chemotherapy, target therapy, and immunotherapy) after treatment discontinuation is summarized by using descriptive statistics such as number of subjects (n), mean, standard deviation, median, quartile (Q1 and Q3), minimum (min), and maximum (max).

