7.1.2. Efficacy evaluation

To evaluate the primary and secondary efficacy endpoints of SHR-1210 in combination with apatinib mesylate in patients with advanced hepatocellular carcinoma as per RECIST v1.1 (Appendix II).

Baseline lesions will be assessed once every 2 cycles during the first 12 treatment cycles (bone scan will be performed if bone progression is suspected or CR is confirmed) and then once every 3 cycles thereafter. Tumor assessments are not affected by treatment discontinuation or delay. Tumor assessments may also be performed if new lesions are suspected. The first PR/CR must be confirmed after 4 weeks \pm 7 days. As per RECIST 1.1, imaging confirmation is required 4-6 weeks after the first documentation of disease progression (except those with rapid progression or significant clinical progression).

For the record and assessment of survival, the subjects will be followed up by telephone for survival once every month after leaving the group until death, lost to follow-up, withdrawal of informed consent, or termination of the study by Hengrui.

Assessments of tumor response include all known or suspected lesions.

Radiographic examination includes CT or MRI scans of the chest, abdomen, or pelvis. Brain CT or MRI is performed for subjects with known or suspected brain metastasis, while bone scan is performed for subjects with known or suspected bone metastasis (**See 7.1 Imaging Examinations for details**).

If discontinuation is indicated by deterioration of overall health in absence of objective evidence of disease progression, such event shall be reported as symptomatic deterioration.

If a subject has not undergone imaging examinations within 4 weeks prior to the end of the study, the subject should undergo an imaging examination for response assessment at the end of the study treatment or upon withdrawal from the study. For subjects with PD demonstrated by non-imaging evidence (intolerability, other conditions), a tumor evaluation is carried out every 3 months until PD, death, or the initiation of other anti-tumor treatments.

Secondary efficacy endpoints in this study include ORR, PFS, DOR, and DCR assessed by the Independent Review Committee (IRC) in accordance with the mRECIST criteria.⁷

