#### **4.1.1. Primary efficacy endpoints**

The primary efficacy endpoint in this study is objective response rate (ORR) assessed by IRC based on RECIST v1.1.

ORR: It refers to the proportion of all subjects whose best overall response (BOR) is assessed as complete response (CR) or partial response (PR) as per RECIST v1.1.

BOR refers to the best overall response assessed by IRC and recorded from the date of first administration to the date of first progression objectively recorded in accordance with RECIST v1.1 or to the date of initiation of new anti-cancer treatment (whichever occurs first). Subjects with first assessment as CR/PR should be reexamined 4 weeks later for confirmation. For subjects who have no recorded progression or initiation of new anti-cancer treatment, the BOR will be determined based on all efficacy assessment results.

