##### **4.1.2.2. Disease control rate (DCR)**

Disease control rate (DCR): It is defined as the proportion of all subjects receiving study treatment, whose BOR is assessed as CR, PR, and SD (SD occurs at least 6 weeks after first administration) by IRC or investigators as per RECIST v1.1 (or mRECIST).

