#### **4.1.2.7. Overall survival (OS)**

Overall survival (OS): It is defined as the time from the date of first administration to death due to any cause.

Censoring rules are as follows:

- If the subject withdraws and is still alive, the censoring date is the last follow-up date when the survival status is obtained.
- If the subject is lost to follow up, the censoring date is the last follow-up date when the survival status is obtained prior to the lost of follow-up.

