### Appendix 1.2 Best Overall Response with CR and PR to be Confirmed

Overall Response at First Time Point	Overall Response at Subsequent Time Point	Best Overall Response
CR	CR	CR
CR	PR	SD, PD, or PR a
CR	SD	SD (provided minimum criteria for SD duration met, otherwise, PD)
CR	PD	SD (provided minimum criteria for SD duration met, otherwise, PD)
CR	NE	SD (provided minimum criteria for SD duration met, otherwise, NE)
PR	CR	PR
PR	PR	PR
PR	SD	SD
PR	PD	SD (provided minimum criteria for SD duration met, otherwise, PD)
PR	NE	SD (provided minimum criteria for SD duration met, otherwise, NE)
NE	NE	NE

Overall Response at First Time Point	Overall Response at Subsequent Time Point	Best Overall Response
CR = complete response, PR = partial response, SD = stable disease, PD = progressive disease, and NE = not evaluable.		
a : If a CR is truly met at first time point, then any disease seen at a subsequent time point, even disease meeting PR criteria relative to baseline, makes the disease PD at that point (since disease must have reappeared after CR). Best response would depend on whether minimum duration for SD is met. However, sometimes CR may be claimed but subsequent scans suggest small lesions were likely still present, so in fact the patient had PR, not CR at the first time point. Under these circumstances, the original CR should be changed to PR and the best response is PR.		

## Appendix 2

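### Overall survival curves split by best overall response start the clock before response is known, so in expectation they favour responders even if response has no effect on survival

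*SAP*

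**What the plan says.** Under SAP 5.4.5, in the FAS, "the overall survival curve is plotted according to different populations and grouped by CR + PR, SD, and PD according to best overall response". Response is IRC-assessed under RECIST v1.1, and the plot is drawn "excluding subjects with the best overall response of NE".

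The clock for OS is set in SAP 4.1.2.7: "It is defined as the time from the date of first administration to death due to any cause".

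The grouping variable is settled afterwards. SAP 4.1.1 has BOR "recorded from the date of first administration to the date of first progression objectively recorded in accordance with RECIST v1.1" or to the start of new anti-cancer treatment. It adds: "Subjects with first assessment as CR/PR should be reexamined 4 weeks later for confirmation". Under SAP Appendix 1.2 an unconfirmed response does not stay in the CR+PR group. For a CR or PR followed by NE, the entry begins "SD (provided minimum criteria for SD duration met, otherwise, NE". The only minimum SD duration given is in the DCR definition (SAP 4.1.2.2): "SD occurs at least 6 weeks after first administration".

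On scan timing, Protocol 7.1.2 says "Baseline lesions will be assessed once every 2 cycles during the first 12 treatment cycles", which is every 8 weeks. Protocol 3.1 and SAP 2.1 instead give an interval of 2 weeks over the same period.

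Neither document gives a landmark, a time-dependent response covariate or a caveat for these curves. SAP 5.4.3 (exploratory analyses) points to 5.4.5, and no test or hazard ratio between BOR groups is planned.

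**The concern.** Patients are sorted by something observed after time zero, and then all their time from zero is credited to the group they ended in. To be in the CR+PR group a patient must be alive at first response and again at the confirming scan. With 8-week scans that is about week 12, or about week 10 at the early edge of the ±7-day windows on scan and confirmation. Until then a death in the CR+PR group is impossible by definition. A patient who responds at week 8 and dies before confirmation has passed the 6-week SD minimum and so moves to SD, taking an early death there.

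The trial has no control arm and ORR is primary, so a reader who wants to know whether response goes with longer life will look at this plot. Some of the separation it shows would arise from the grouping rule alone.

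**Working it through.** The documents give no figure for these curves, so there is nothing of the plan's own to reproduce. The check asks what the plot would show if response had no effect on survival.

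**Inputs from the documents.** Scans every 8 weeks (Protocol 7.1.2); confirmation 4 weeks later (SAP 4.1.1); NE excluded (SAP 5.4.5); 30.4375 days per month (SAP 5.4.2.7).

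**Assumptions.** Exponential OS with the same median m for everyone; latent response in 28% (the design rates are 25% and 30%); first response at weeks 8/16/24 in 60/30/10%, or all at week 8; death before the first scan gives NE; no censoring.

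**Formulas.** S(t) = 0.5^(t/m), t in months. Weeks 8, 12, 20 and 28 are 1.84, 2.76, 4.60 and 6.44 months.
- Share in CR+PR: 0.28 × Σ p × S(confirmation time).
- Share in other evaluable groups: S(1.84) minus the CR+PR share.
- After the last confirmation, the proportions still alive are 0.28 × S(t) and 0.72 × S(t). Each median is where that equals half the group's share.

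**m = 10, timing 60/30/10%.** S(1.84) = 0.880, S(2.76) = 0.826, S(4.60) = 0.727, S(6.44) = 0.640.
- CR+PR share: 0.28 × (0.6×0.826 + 0.3×0.727 + 0.1×0.640) = 0.28 × 0.778 = 0.218. Median: S(t) = 0.778/2 = 0.389, so t = 10 × log2(1/0.389) = **13.6 months**.
- Others: 0.880 − 0.218 = 0.662. Median: S(t) = 0.331/0.72 = 0.460, so t = **11.2 months**.
- If NE were kept with the others: 1 − 0.218 = 0.782; S(t) = 0.391/0.72 = 0.543, so t = 8.8 months.

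The gap is 2.4 months with NE excluded and 4.8 with NE kept.

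**Same formulas, other inputs (NE excluded):**

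| True median | Timing of first response | CR+PR | Others |
|---|---|---|---|
| 10 | 60/30/10% at weeks 8/16/24 | 13.6 | 11.2 |
| 15 | 60/30/10% at weeks 8/16/24 | 18.6 | 16.2 |
| 10 | all at week 8 | 12.8 | 11.5 |
| 26.4 | all at week 8 | 29.2 | 27.9 |

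Simulation with the same inputs agrees to within 0.1 month.

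**The three curves as the SAP draws them.** A simulation of 600,000 patients per scenario used 30% latent response, 25% PD at first scan, and death independent of the tumour process. The OS scenarios are anchored on the Protocol's background: median 9.8 months (apatinib 750 mg), and 12-month survival of 58% and 73% (nivolumab), which give exponential medians of 15.4 and 26.4. The columns run from all responses at the first scan to slower responses (mean latent time 22.9 weeks).

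| True median | CR+PR/SD/PD medians, early | CR+PR/SD/PD medians, slower | HR CR+PR vs SD |
|---|---|---|---|
| 9.8 | 12.6/11.0/11.6 | 15.3/9.9/11.6 | 0.90 to 0.73 |
| 15.4 | 18.1/16.6/17.2 | 21.2/15.0/17.2 | 0.93 to 0.79 |
| 26.4 | 29.2/27.7/28.2 | 32.2/25.7/28.3 | 0.96 to 0.86 |

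Under the conflicting 2-week interval, the HR for CR+PR vs SD runs from 0.91 to 0.67.

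**Landmark check, null data.** With status as confirmed by week 16 and OS counted from week 16, medians are 10.0 vs 10.0 months (m = 10). A week-24 landmark gives hazard ratios of 0.99 to 1.00. If a response first seen at week 16 and confirmed at week 20 is allowed to count at the week-16 landmark, bias returns: 10.3 vs 9.9.

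**The case against.** The strongest reply is that little depends on this figure. It sits among waterfall, swimmer and spider plots, in a section the SAP treats as exploratory, with no test attached. Where the SAP wants a test it says so, as for PD-L1 in 5.6.3. Efficacy is decided by the lower confidence limit of ORR (SAP 3), and OS itself is estimated without grouping by response (SAP 5.4.2.7 and 5.4.2.8). All of that stands and limits the importance of the point. It does not make the grouping rule sound.

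Three stronger readings are tempting, and the documents do not support them.

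- A reader might infer that responders must come out ahead. The bias holds in expectation only. In single null trials with 8-week scans, the CR+PR hazard was the lower one in about 56–95% of runs, against 50% without bias. Had a 5% test been planned, false positives would have been about 4–20% at n = 120 and 5–30% at n = 176 (120 + 56).
- A reader might count the exclusion of NE as part of the fault. It works the other way: it removes deaths before the first scan from every curve and, in the worked case, halves the gap.
- A reader might take the plot as the plan's evidence that response brings survival benefit. Neither document gives it that role.

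It is also fair to object that size depends on response timing, which no document gives. If nearly all responses come at the first scan and survival is long, the spurious HR is about 0.96.

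**Conclusion.** The concern holds for this figure. OS from first dose, grouped by a later and confirmed response, favours CR+PR in expectation when response has no effect on survival. In the worked cases the spurious difference in medians against other evaluable patients is about 1.3 to 2.5 months. Against SD alone the spurious HR lies between 0.96 and 0.73 with 8-week scans. These sizes rest on assumed exponential survival, response rate, response timing and no censoring; the direction in expectation follows from the grouping rule. The primary ORR analysis, the decision rule and the ungrouped OS estimates are untouched.

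The 2-week and 2-cycle imaging intervals contradict each other and must be reconciled, because the earliest possible confirmation date depends on them.

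**What to change.** Replace the figure in SAP 5.4.5, or set beside it as the version to interpret, a landmark analysis:

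- FAS patients alive and in follow-up at a prespecified landmark: week 16, with week 24 as sensitivity.
- Groups by IRC status using only information dated up to the landmark, with CR or PR counted only if already confirmed by then. State in advance where patients with no evaluable scan by the landmark go.
- OS plotted from the landmark.
- Optionally, a Cox model with confirmed response as a time-dependent covariate.

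If the present curve is kept, label it as not showing an effect of response on survival. The landmark version also needs care in wording: it removes the immortal time, but responders may still differ from others in prognosis.

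The cost is SAP wording and one re-programmed figure, with no new data. Deaths before the landmark leave this figure: 1 − 0.5^(3.68/m) is 9% at week 16 for a true median of 26.4 months and about 22% for 10 months. Responses confirmed after the landmark count as non-response in it. Under the 60/30/10% timing that is 40% of latent responders at week 16 and 10% at week 24, which is the reason for the second landmark.

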## **5.5. Safety Analysis**

All safety analyses are conducted based on safety analysis set.

### **5.5.1. Extent of exposure**

Extent of exposure mainly for drug exposure duration, planned treatment time, cycle length, actual cumulative dose per cycle, actual cumulative doses of all cycles, actual dose intensity per cycle, actual dose intensity, relative dose intensity per cycle, and relative dose intensity of SHR-1210 and apatinib is summarized by using mean, standard deviation, median, maximum, minimum, and quartile, and the medication intensity per cycle and overall medication intensity for each subject are listed.

In addition, only the number of use of SHR-1210 is calculated and summarized by using mean, standard deviation, median, maximum, and minimum. The number and percentage of subjects who receive SHR-1210 treatment for  $\geq 6$  months and  $\geq 12$  months and subjects who receive apatinib treatment for  $\geq 6$  months and  $\geq 12$  months are calculated, respectively.

See [Table 1](#) for the specific definition rules of derived variables of study drugs SHR-1210 and apatinib.

**Table 1. Derived variables of SHR-1210 and Apatinib**

Variable	SHR-1210	Apatinib
Protocol-specified method of administration	Administration once per two weeks, 200 mg or 3 mg/kg each time, and every 4 weeks for a cycle	Administration once per day, 250 mg each time, and every 4 weeks for a cycle
Duration of drug exposure (days)	Date of last administration - date of first administration + 14	Date of last administration - date of first administration + 1
Planned duration of treatment (days)	Date of last administration - date of first administration + 14	Date of last administration - date of first administration + 1
Cycle length (weeks)	Except for the last cycle: (Actual starting date of next cycle - 1 - actual starting date of the cycle + 1) / 7; Last cycle: (Date of last administration + 14 - actual starting date of the cycle) / 7	Except for the last cycle: (Actual starting date of next cycle - 1 - actual starting date of the cycle + 1) / 7; Last cycle: (Date of last administration + 1 - actual starting date of the cycle) / 7
Actual cumulative dose per cycle (mg)	Actual administration dose (mg) during a cycle is summarized, and each actual administration dose is recorded in CRF	
Actual cumulative doses of all cycles (mg)	Actual administration doses (mg) during all cycles are summarized	
Planned cumulative dose per cycle (mg)	200 (mg) × 2 = 400 (mg)*	250 (mg) × 28 = 7000 (mg)*
Actual dose intensity per cycle (mg/4-week cycle)	Actual cumulative dose per cycle (mg) / [cycle length (weeks) / 4]	
Actual dose intensity (mg/4-week cycle)	Actual cumulative doses of all cycles (mg) / [planned treatment time (weeks) / 4]	
Planned dose intensity per cycle (mg/4-week cycle)	Planned cumulative dose per cycle (mg) / [1 (4-week cycle)] = 400 (mg/4-week cycle)**	Planned cumulative dose per cycle (mg) / [1 (4-week cycle)] = 7000 (mg/4-week cycle)
Planned dose intensity (mg/4-week cycle)	400 (mg/4-week cycle)***	7000 (mg/4-week cycle)
Relative dose intensity per cycle (%)	100 × [Actual dose intensity per cycle (mg/4-week cycle)] / [Planned dose intensity per cycle (mg/4-week cycle)]	
Relative dose intensity (%)	100 × [Actual dose intensity (mg/4-week cycle)] / [Planned dose intensity (mg/4-week cycle)]	

\*: If the baseline weight of the subject is < 50 kg, the planned cumulative dose per cycle (mg) = 3 (mg/kg) × baseline weight (kg) × 2 = 6 × baseline weight (mg);

\*\*: If the baseline weight of the subject is < 50 kg, the planned dose intensity per cycle (mg/4-week cycle) = 6 × baseline weight (mg/4-week cycle)

\*\*\*: If the baseline weight of the subject is < 50 kg, the planned dose intensity (mg/4-week cycle) = 6 × baseline weight (mg/4-week cycle).

### 5.5.2. Adverse events

All AEs are encoded by using MedDRA v24.0 and graded using NCI-CTCAE v4.03. For the same SOC and/or PT, multiple cases of the same events occurred in one subject will be counted only once. For the same AE reported in one subject multiple times but varying in CTCAE grade, the AE of the greatest grade will be enumerated.

Treatment-emergent adverse events (TEAEs) are defined as any adverse events (AEs) that are new or worse than those at baseline (before treatment) after initiation of the study drugs. Only TEAEs will be summarized, and all AEs will be listed.

Drug-related TEAE (ADR) is defined as TEAE having the causal relationship of "*treatment-related*" with study drugs. In this trial, the definition of "*treatment-related*" is as follows: It refers to the relationship with the study drugs: related, possibly related, and unassessable. If the relationship between the AE and the study drugs is missing, the AE will be considered as an ADR.

AEs will be ranked from high to low according to the proportion of SOC/Cluster occurrence (total populations receiving the treatment), from high to low according to the proportion of PT under SOC (total populations receiving the treatment), and in alphabetical order if the incidences of at least 2 PTs are equal. If there is no AE under an SOC/Cluster or PT, the analysis will not be performed. Refer to Appendices 4 and 5 for the definition of Cluster classification.

In AE summary table, AEs after study drug treatment are analyzed according to the population, and the frequency and proportion are used for statistical description. AEs will be summarized using descriptive statistics according to Hengrui's Statistical Analysis Reporting Standards, including but not limited to the following contents:

- Any TEAE
- Treatment-related TEAE
- Any TESAE
- Treatment-related TESAE
- Grade  $\geq 3$  TEAE according to CTCAE grading
- Grade  $\geq 3$  treatment-related TEAE according to CTCAE grading
- Any TEAE  $\geq 5\%$
- Treatment-related TEAE  $\geq 5\%$
- TEAE leading to SHR-1210 treatment discontinuation and interruption

- TEAE leading to apatinib treatment discontinuation, treatment interruption, and dose reduction
- TEAE leading to death
- TEAE of special interest (AESI, the preferred term for AE provided by medical monitor, see Appendix 2 for details; other Grade  $\geq 3$  immune-related adverse events (irAEs): meeting irAE definition requirements and Grade  $\geq 3$  according to CTCAE v4.03)
- Immune-related TEAE (irAE, including two categories: 1) AE that the investigators determine to be related to SHR-1210 (including definitely related, possibly related, and indeterminable) and corrected with glucocorticoid drugs (except reactive capillary endothelial proliferation); 2) other irAEs that the investigators determine to be related to SHR-1210 without the use of glucocorticoids, with the preferred term for AE provided by medical monitor, see Appendix 3 for details)
- The selected TEAE (the preferred term for AE provided by medical monitor, see Appendix 4 for details)
- The selected TEAE that the investigators determine to be related to SHR-1210 (the preferred term for AE provided by medical monitor, see Appendix 5 for details) and glucocorticoid utilization rate
- No subject with TEAE leading to interruption, dose reduction, and termination of two drugs
- TEAE leading to treatment interruption (apatinib or SHR-1210)
- TEAE leading to treatment termination of two drugs

The incidence of AE is calculated based on the number of subjects having an AE, instead of the number of AE episodes.

AESIs include:

- Grade  $\geq 3$  infusion reaction
- Grade  $\geq 2$  diarrhea/colitis, uveitis, and interstitial pneumonia
- Other Grade  $\geq 3$  irAEs
- Liver enzyme abnormal event: ALT, AST, and total bilirubin (TBIL) are abnormal against baseline
- Grade 4 amylase or lipase increased
- Reactive capillary endothelial proliferation

Among them, the specific definition of liver enzyme abnormal events is as follows:

Baseline Period	Normal (AST/ALT and TBIL)	Abnormal (AST/ALT/TBIL)
Treatment Period	ALT or AST $\geq 3 \times \text{ULN}$ with TBIL $\geq 2 \times \text{ULN}$ and ALP $\leq 2 \times \text{ULN}$ and without hemolysis	AST or ALT $\geq 2 \times \text{baseline level}$ , and $\geq 3 \times \text{ULN}$ or AST or ALT $\geq 8 \times \text{ULN}$ with TBIL increase $\geq 1 \times \text{ULN}$ or TBIL $\geq 3 \times \text{ULN}$

The selected AEs are analyzed separately. For each selected AE, the time to first event (weeks) is summarized in the form of continuous variables, that is, mean, standard deviation, median, maximum, minimum, and quartile (Q1 and Q3) are used for the summary. The greatest grade and the measures taken to study drugs are summarized in the form of categorical variables. The events are also summarized according to factors such as TEAE severity and TEAE occurrence cycle, respectively. The number and percentage of subjects who experience each selected AE and have been resolved are summarized.

The calculation method for the cycle length of TEAE which occurs is:

(Starting date of TEAE - date of first administration + 1) / 28 + 1, and the integer part will be retained;

Time to first event (weeks) = (date of first event occurrence - date of first administration + 1) / 7.

All AEs will be listed. Treatment-related AEs, AEs that result in treatment termination, AEs that result in treatment delay or dose reduction, and death will be listed separately.

